Participants randomized to the PSL arm will receive separate infusions of partially HLA -matched PSL cells (each administered via central or peripheral intravenous [IV] infusion over approximately minutes as a slow push).

The placebo arm will receive separate IV infusions of cryopreservation media (without cells).

The second infusion (PSL or placebo) will occur approximately (± 3) days after the first infusion. Administering the second infusion as early as feasible within this window is encouraged. Participants who weigh <40 kg at the time of screening will receive PSL cells

(or placebo), while participants who weigh ≥40 kg at the time of screening will receive PSL cells (or placebo).

EFFICACY VARIABLES:

Primary Efficacy Endpoint

The primary endpoint is the time to resolution of macroscopic hematuria in participants with documented BK viruria. A supplementary analysis will evaluate the time to resolution of macroscopic hematuria in participants with any virus-associated HC. Resolution of macroscopic hematuria is defined as resolution to Grade 0 or 1 on the Bedi scale as assessed by the Investigator on 2 consecutive visual urine assessments >2 days apart without continuous bladder irrigation or nephrostomy tubes. However, if a participant has nephrostomy tubes that are capped, Bedi assessments may be performed, including for the purpose of assessing for resolution. A healthcare provider (HCP) on the study team (including a home health provider) may perform the visual urine assessment, but it is the Investigator's responsibility to determine the Bedi score. Grade 0 requires no detectable blood by urinalysis; Grade 1 hematuria requires confirmation of resolution by urinalysis results of ≤ 100 RBCs/high power field (HPF). Time to resolution will be calculated starting from the date of randomization. The second urine assessment is required to establish resolution, but for the calculation of time to resolution, the date of the first of these two visual urine assessments without macroscopic hematuria (by the Hemostick® visual scale for outpatients; by the Bedi scale for inpatients) will be used. Participants will be followed for the primary endpoint for a maximum of 24 weeks from the date of randomization.

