7 EFFICACY ASSESSMENTS

The primary endpoint is the time to resolution of macroscopic hematuria in participants with documented BK viruria. Resolution of macroscopic hematuria is defined as resolution to Grade 0 or 1 on the Bedi scale⁴⁷ as assessed by an HCP on the study team on 2 consecutive visual urine assessments ≥ 2 days apart without continuous bladder irrigation or nephrostomy tubes; Grade 1 hematuria requires confirmation of resolution by urinalysis results of ≤ 100 RBCs/high power field (HPF). If a participant has nephrostomy tubes that are capped, Bedi assessments may be performed, including for the purpose of assessing for resolution. Details of the macroscopic hematuria assessment are provided in Section 7.1.

The key secondary endpoint is the time to resolution of bladder pain as measured by age-appropriate COAs. Resolution of bladder pain is defined as participants achieving a score on the relevant COA that does not exceed "mild pain" without use of prescription pain medications or the use of supportive bladder care.

Mild bladder pain is defined as:

- In participants ≥12 years of age: a score ≤3 on the worst daily pain question from the Bladder Pain/Interstitial Cystitis Symptom Diary (BPIC SD).
- In participants 3 to 11 years of age: a score ≤2 on the Wong-Baker FACES® Pain Rating Scale.

This endpoint will not be assessed in participants <3 years of age as there is no COA that has been validated for this purpose. Instead, data regarding pain behaviors will be collected in this age group using the Patient-Reported Outcomes Measurement Information System® (PROMIS) Parent Proxy Pain Behavior Short Form.

Additional secondary efficacy endpoints include the following:

- Number of days in the hospital (for any reason including, but not limited to, HC) over the 24-week study period.
- Time to resolution of viremia for all target viruses (ie, BKV, AdV, CMV, HHV-6, JCV, and/or EBV) over the 24-week study period (only for participants with detectable viremia at baseline).
 Evaluation of this endpoint will be based on viremia quantitation performed at the central laboratory. Resolution of viremia will be defined by the lower limits of detection of the assays used.
- Average daily bladder pain (including lower abdominal pain, bladder-related pressure, and/or spasm pain or dysuria) over the initial 6 weeks following randomization.

The exploratory efficacy endpoints include the following:

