9.2.1 Analysis of Efficacy

9.2.1.1 Primary Efficacy Endpoint Analysis

The primary endpoint is the time to resolution of macroscopic hematuria in participants with documented BK viruria. Resolution of macroscopic hematuria is defined as resolution to Grade 0 or 1 on the Bedi scale⁴⁷ on 2 consecutive urine assessments \geq 2 days apart without continuous bladder irrigation or nephrostomy tubes; Grade 1 requires confirmation of resolution by urinalysis results of \leq 100 RBCs/HPF. If a participant has nephrostomy tubes that are capped, Bedi assessments may be performed, including for the purpose of assessing for resolution.

The objective is to demonstrate the superiority of PSL therapy to placebo with respect to the time to resolution of macroscopic hematuria.

The primary efficacy analysis will be conducted after all participants have completed 24 weeks of follow up or discontinued from the study. At the primary analysis, the PSL group will be compared to the placebo group in the BK ITT Population using a stratified log-rank test based on the stratification factors at randomization. The study will be considered a success if the one-sided p-value from the stratified log-rank test comparing treatment to control is less than 0.0147 (reduced from 0.025 due to inclusion of an interim analysis based on Pocock method). A supplementary efficacy analysis based on the overall ITT Population will also be conducted. Time to resolution will be calculated from the time of randomization to the date of the first resolution of macroscopic hematuria (see Section 7.1). Participants not observed to achieve resolution will be considered censored at their last follow-up for the primary endpoint. Definitive therapies to stop bladder bleeding, such as cystectomy, bladder vessel embolization, cauterization, application of fibrin "glue" preparations, or formalin instillation are permitted but will be considered treatment failures for the primary endpoint of time to resolution of macroscopic hematuria and will be censored at 24 weeks. The detailed censoring rules will be specified in the SAP.

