APPENDIX A: SCHEDULE OF PROCEDURES

		Т	I								I
Study Visit/Week											
Visit Window (Days)	NA	NA	NA	±3	±3	±3	±3	±3	±3	±28	±28
Study Procedures											
Pre-screening informed											
consent/assent	X										
Informed consent/assent		X									
[4]											
I/E criteria	X	X									
Demographics [5]		X									
Medical history		X									
Prior and concomitant											
medications [6]											
Adverse events [7]											→
Complete physical		X		X	X	X	X	X	X	X	X
examination [8]				21.		71	21	21	21.	71	
Height and weight [9]		X	X		X						X
Vital signs and pulse			X	X	X	X	X	X	X	X	X
oximetry [10]			71			- 11	2 .	71	21		71
Clinical outcome		-				See Apper	ndix B				→
assessments [11]			ı	1	1	11	1	1	1	1	1
Documentation of HLA		X									
typing [5,12]		V [14]	X	X	X	X	X	X	X	X	X
Hematology [13]		X [14]									
Clinical chemistry [15]	37	X [14]	X	X	X	X	X	X	X	X	X
Viral loads in urine [15]	X	X [14]	X	X	X	X	X	X	X	X	X
Viral loads in blood [13,			X	X	X	X	X	X	X	X	X
15]		37	V		V						37
Pregnancy test [16]		X	X		X						X
FSH [17]		X								 	

Study Visit/Week	Pre-										
Visit Window (Days)	NA	NA	NA	±3	±3	±3	±3	±3	±3	±28	±28
Study Procedures											
Visual assessment of urine by Bedi grading with urinalysis		X	•	(Day 42	ne, then 3 × 2) or until reline, then 1 :	esolution, t	hen 1 × per	week		Inpatient week [18 apart resolution per v Outpation per week resolution	y 43): s: 2 × per] ≥2 days then 1 × week tents: 1 ×
Visual assessment of urine by Hemostick (outpatients only)			At baselin		ly through				solution	2 × per days ap resolution	week 7 week ≥2 art until then 1 × week
Collection of PBMCs for banking of human genetic DNA and plasma [13, 19]			X	X	X	X	X		X	X	X
Acute GVHD evaluation [20]		X	X	X	X		X		X	X	X
Chronic GVHD evaluation [20]			X							X	X
Randomization [21] Distribution of subject cards			X X								
Study treatment administration [22]			X		X						
Post-infusion monitoring [23]			X		X						
12-Lead ECG		X	X [24]		X [24]						X

- Note: Study visits should occur at the study site. If this is not possible, home health visits may be performed as agreed with the Sponsor.
- 1. Participants may complete an optional Pre-Screening Visit that will be conducted from 14 days prior to the randomization visit to the day of the randomization visit. A separate Pre-Screening consent form is available for this purpose.
- 2. All screening and baseline assessments must be performed prior to study treatment administration.

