APPENDIX C: BLOOD VOLUME TABLE AND SAMPLING SCHEDULE

Study blood sampling volumes and sampling schedule by body weight are described in the tables below.

Blood Volume (mL) Drawn for Study Assessments: Adult and Pediatric Participants ≥40 kg

Study Week	Baseline	Week 1	Week 2	Week 3	Week 4	Total, First 4 Weeks	Week 5	Week 6	Total, First 8 Weeks	Week 12	Week 24	Total, 24 weeks
Study Day	0	7	14	21	28	NA	35	42	NA	84	168	NA
Visit Window (Days)	NA	±2	±3	±2	±3	NA	±3	±3	NA	±28	±28	NA
Assessment												
Hematology	3	3	3	3	3	15	3	3	21	3	3	27
Clinical chemistry	7	7	7	7	7	35	7	7	49	7	7	63
Viral load (plasma)	24	24	24	24	24	120	24	24	168	24	24	216
EBV viral load (PBMC)	8	8	8	8	8	40	8	8	56	8	8	72
Banked PBMC DNA	8	8	8	8	8	40	0	8	48	8	8	64
Totals	50	50	50	50	50	250	42	50	342	50	50	442

DNA = deoxyribonucleic acid; EBV = Epstein-Barr virus; NA = not applicable: PBMC = peripheral blood mononuclear cell.

Blood Volume (mL) Drawn for Study Assessments: Pediatric Participants ≥30 kg to <40 kg

Study Week	Baseline	Week 1	Week 2	Week 3	Week 4	Total, First 4 Weeks	Week 5	Week 6	Total, First 8 Weeks	Week 12	Week 24	Total, 24 weeks
Study Day	0	7	14	21	28	NA	35	42	NA	84	168	NA
Visit Window (Days)	NA	±2	±3	±2	±3	NA	±3	±3	NA	±28	±28	NA
Assessment												
Hematology	2	2	2	2	2	10	2	2	14	2	2	18
Clinical chemistry	4	4	4	4	4	20	4	4	28	4	4	36
Viral load (plasma)	12	12	12	12	12	60	12	12	84	12	12	108
EBV viral load (PBMC)	8	8	8	8	8	40	8	8	56	8	8	72
Banked PBMC DNA	8	8	8	8	8	40	0	8	48	8	8	64
Totals	34	34	34	34	34	170	26	34	230	34	34	298

DNA = deoxyribonucleic acid; EBV = Epstein-Barr virus; NA = not applicable; PBMC = peripheral blood mononuclear cell.

Blood Volume (mL) Drawn for Study Assessments: Pediatric Participants ≥20 kg to <30 kg

Study Week	Baseline	Week 1	Week 2	Week 3	Week 4	Total, First 4 Weeks	Week 5	Week 6	Total, First 8 Weeks	Week 12	Week 24	Total, 24 weeks
Study Day	0	7	14	21	28	NA	35	42	NA	84	168	NA
Visit Window (Days)	NA	±2	±3	±2	±3	NA	±3	±3	NA	±28	±28	NA
Assessment												
Hematology	2	2	2	2	2	10	2	2	14	2	2	18
Clinical chemistry	4	4	4	4	4	20	4	4	28	4	4	36
Viral load (plasma)	12	12	12	12	12	60	0	12	72	12	12	96
EBV viral load (PBMC)	8	0	8	0	8	24	0	8	32	8	8	48
Banked PBMC DNA	8	8	8	8	8	40	0	8	48	8	8	64
Totals	34	26	34	26	34	154	6	34	194	34	34	262

DNA = deoxyribonucleic acid; EBV = Epstein-Barr virus; NA = not applicable; PBMC = peripheral blood mononuclear cell.

Blood Volume (mL) Drawn for Study Assessments: Pediatric Participants ≥10 kg to <20 kg

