3.1.9 Data Collected After End of Study

Data collected after the end of study will not be included in the summary tables but will only be presented in listings.

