APPENDIX A: ANALYSIS WINDOWS

Table 1.1 Analysis	Visit Window for	Selected ePRO En	dpoints (Dail	y for First Six Weeks)
--------------------	------------------	------------------	---------------	------------------------

Analysis Visit	Target Analysis Day	Low Analysis Day	High Analysis Day
Day 1/Baseline	1		1
Day 2	2	2	2
Day 42	42	42	42
Week 7	50	43	49
Week 23	162	156	162
Week 24	169	163	

Table 1.2 Analysis Visit Window for Selected ePRO Endpoints (Weekly for First Six Weeks)

Analysis Visit	Target Analysis Day	Low Analysis Day	High Analysis Day
Day 1/Baseline	1		1
Week 1	8	2	8
Week 2	15	9	15
Week 3	22	16	22
Week 4	29	23	29
Week 5	36	30	36
Week 6	43	37	43
Week 7	50	44	50
Week 23	162	156	162
Week 24	169	163	

Table 2. Analysis Visit Window for EQ-5D-Y Proxy Version 1, EQ-5D-Y and EQ-5D-5L

Analysis Visit	Target Analysis Day	Low Analysis Day	High Analysis Day
Day 1/Baseline	1		1
Week 1	8	2	8
Week 2	15	9	15
Week 3	22	16	22
Week 4	29	23	29
Week 5	36	30	36
Week 6	43	37	43
Week 8	57	51	57
Week 12	85	79	85
Week 16	113	107	113
Week 24	169	163	

Table 3. Analysis Visit Window for Viral Load (in Blood and Urine), Vital Signs, Pulse Oximetry, Clinical Chemistry and Hematology

Analysis Visit	Target Analysis Day	Low Analysis Day	High Analysis Day
Day 1/Baseline	1		1
Week 1	8	2	11
Week 2	15	12	18
Week 3	22	19	25

Analysis Visit	Target Analysis Day	Low Analysis Day	High Analysis Day
Week 4	29	26	32
Week 5	36	33	39
Week 6	43	40	63
Week 12	85	64	126
Week 24	169	>126	

Table 4. Analysis Visit Window for 12-Lead ECG and Weight

Analysis Visit	Target Analysis Day	Low Analysis Day	High Analysis Day
Day 1/Baseline	1		1
Week 2	15	2	92
Week 24	169	>92

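### The ±28-day Week 24 window leaves the hospital-days count without a fixed 24 weeks, the SAP censoring rules omit the 24-week cap, and a compliant early Week 12 visit can be discarded

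*Protocol*

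**What the plan says.** **Length of follow-up.** Protocol 9.2.1.1 times the main analysis: "The primary efficacy analysis will be conducted after all participants have completed 24 weeks of follow up or discontinued from the study". The Protocol Synopsis (Primary Efficacy Endpoint), repeated in SAP 2.3.1, sets a cap: "Participants will be followed for the primary endpoint for a maximum of 24 weeks from the date of randomization".

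**Visit schedule.** Protocol Appendix C lists the days as "Study Day 0 7 14 21 28 NA 35 42 NA 84 168 NA" and the tolerances as "Visit Window (Days) NA ±2 ±3 ±2 ±3 NA ±3 ±3 NA ±28 ±28 NA". Week 12 is therefore Day 84 and Week 24 is Day 168, each with 28 days either way. Appendix A shows the same tolerance for its last two visits. No visit is scheduled after Week 24.

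**Hospital days.** Protocol Section 7 and SAP 2.3.2 define the endpoint: "Number of days in the hospital (for any reason including, but not limited to, HC) over the 24-week study period". Protocol 9.2.1.3 and SAP 3.4.3 place it in the testing hierarchy, in a linear regression whose only terms are treatment and the stratification factors.

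**Censoring.** SAP 3.4.1 censors non-resolvers at their own last follow-up in the study. Treatment failures (definitive therapy after randomization, death, non-PSL virus-specific T cells) are censored at the latest follow-up reached by anyone in the trial. Protocol 9.2.1.1 ties non-resolvers to last follow-up for the primary endpoint, and censors definitive-therapy failures at 24 weeks. SAP 3.1.9 adds: "Data collected after the end of study will not be included in the summary tables".

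**Analysis windows.** SAP Appendix A, Table 3 ("Analysis Visit Window for Viral Load (in Blood and Urine), Vital Signs, Pulse Oximetry, Clinical Chemistry and Hematology") assigns SAP Days 40 to 63 to Week 6 (target 43), Days 64 to 126 to Week 12 (target 85), and all later days to Week 24. Under SAP 3.1.3, when two visits share a window the one nearer the target is kept.

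**The concern.** A count over 24 weeks is comparable between participants only if each completer is observed for the same 24 weeks, or if the model allows for unequal observation. Here the visit schedule does not ensure the first and the regression does not do the second. Two fully compliant participants with the same hospital use per week could contribute different totals.

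For the primary endpoint, the risk is that the analysis is programmed from SAP 3.4.1, which gives no instruction to stop at 24 weeks, so that resolutions after the cap count as events.

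For the Table 3 variables, a visit held within the Protocol's tolerance can be removed by the SAP's own assignment rule, leaving a gap that looks like a missed visit.

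**Working it through.** **1. Week 24 window.** 168 − 28 = 140 and 168 + 28 = 196. In weeks, 140/7 = 20 and 196/7 = 28. Relative to 168 days the limits are 140/168 = 0.833 and 196/168 = 1.167, or 16.7% either side. The longest permitted period is 196/140 = 1.4 times the shortest. This is the period of observation only if follow-up stops at the final visit. The documents do not say that it does, but nothing on-site is scheduled later.

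**2. Effect on the primary.** Inputs from Protocol 9.2.4 and SAP 2.2.3: 105 participants; exponential medians of 12 and 6 weeks; dropout d by Week 24 of 10% (Protocol) or 20% (SAP); one-sided 0.0147 at each of two looks (Protocol) or 0.025 (SAP). Assumptions: the allocation ratio is redacted, so 1:1 and 2:1 are both shown, and the Protocol's first look is put at information fraction 60/105.

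Event hazard λ = ln 2 / median; censoring hazard γ = −ln(1 − d)/24; probability of an observed event by week T = λ/(λ + γ) × [1 − exp(−(λ + γ)T)]. With D expected events and a fraction a on PSL, power = Φ(√(D·a(1 − a)) × ln 2 − z). The Protocol figures use the two-look version.

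Example, SAP inputs, 1:1, T = 24: the event probabilities are 0.689 (placebo) and 0.879 (PSL), so D = 52.5 × (0.689 + 0.879) = 82.3. Power = Φ(√(82.3 × 0.25) × 0.693 − 1.960) = Φ(1.184) = 88.2%.

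| Inputs | Stated power | 20 weeks | 24 weeks | 28 weeks |
|---|---|---|---|---|
| Protocol, 2:1 | 83.8% | 81.5% | 83.4% | 84.7% |
| Protocol, 1:1 | 83.8% | 84.2% | 86.3% | 87.7% |
| SAP, 2:1 | 86.4% | 84.0% | 85.6% | 86.7% |
| SAP, 1:1 | 86.4% | 86.4% | 88.2% | 89.3% |

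At 2:1 the 24-week column comes within 1 point of both stated figures. A log-rank simulation gave 80.6% (Protocol) and 83.0% (SAP) at 2:1, and 86.7% and 88.4% at 1:1, so the stated figures lie between the two ratios. The stated power is not in dispute. Moving every participant from 24 to 20 or 28 weeks changes it by about 2 points at most.

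**3. Censoring rules side by side.** If the 24-week cap is applied, no event occurs after Day 168, and censoring failures at 24 weeks or later gives the same log-rank result. If it is not applied, follow-up can reach Day 196, later resolutions count as events, and failures remain in the risk sets throughout. The two documents agree only if the cap is programmed, and SAP 3.4.1 does not say to do so.

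**4. Week 12 window.** 84 − 28 = 56 and 84 + 28 = 112, so 57 days are permitted. The Protocol calls the day of randomization and first dose Day 0 and the SAP calls it Day 1 (SAP 3.1.1, 3.1.2), so SAP Day = Protocol Day + 1 when both fall on the same day. Protocol Days 56 to 62 become SAP Days 57 to 63, inside the Week 6 window: 7 of 57 days (12%).

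An on-time Week 6 visit (Day 42 ± 3, SAP Days 40 to 46) is at most 3 days from the target of 43. The early Week 12 visit is 57 − 43 = 14 to 63 − 43 = 20 days away. The on-time visit is kept, the early one is dropped, and Week 12 has no value. Permitted Week 24 visits (SAP Days 141 to 197) all map to Week 24.

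**The case against.** The strongest reply is that a visit tolerance does not shorten follow-up. Protocol 3.1 and SAP 2.2.1 say participants are followed for 24 weeks after first infusion. Patient-reported outcomes run weekly to Week 24, and unresolved hematuria is graded at least weekly after Week 6. Protocol 10.3 defines the end of study for the trial as a whole, and SAP 3.1.9 gives no participant-level day. The log-rank test accommodates unequal censoring. The windows are the same in both blinded arms, so the result is noise and not an evident bias. Hospital days are tested fifth, after four earlier successes.

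Most of this stands, and it limits the point:

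- A reader might infer that the 24-week endpoints in general, including the primary, run to 28 weeks. The documents do not support that. Primary follow-up is capped at 24 weeks from randomization, and SAP 3.4.3 already reports survival by Week 24.
- A reader might infer that an early Week 12 visit is analysed as Week 6. That happens only when no closer Week 6 visit exists. Otherwise the visit is lost.
- That the Week 24 visit closes participation is inferred, not stated.

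The reply does not settle hospital days. No text provides for collecting them between an early final visit and Day 168, or for stopping the count at Day 168 after a late one, and the regression does not adjust for the difference. Nor does it answer the missing cap in SAP 3.4.1 or the Table 3 overlap.

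**Conclusion.** The point holds in three limited parts.

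- **Hospital days.** A formally tested raw count has no stated cut-off and may cover 140 to 196 days, if follow-up ends at the final visit. These are the extremes. The documents give no distribution of visit timing or of hospital days, so the added variance cannot be sized.
- **Primary censoring.** The cap exists but the SAP censoring rules do not carry it, and Protocol and SAP differ on where definitive-therapy failures are censored. A reading that this threatens the trial's power is not supported: even if everyone stopped at Week 20 the loss is about 2 points or less.
- **Week 12 data.** Visits on 7 of 57 permitted days fall in the Week 6 window and, with an on-time Week 6 visit, leave Week 12 empty. This concerns Table 3 variables only (viral load, vital signs, pulse oximetry, chemistry, hematology). The primary, bladder pain and hospital days are not affected. The day mapping assumes randomization and first infusion on the same day.

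**What to change.** 1. In Protocol Appendices A and C, narrow the early side of the Week 24 window, for example to −3 days as at Week 6, and keep the late side. An analysis cut alone cannot recover weeks that were never observed. The cost is that sites lose the option of an early final visit.
2. In the SAP, state that hospital days and primary-endpoint censoring, including treatment failures, are cut at 24 weeks from randomization, and that 24-week safety summaries are cut at 24 weeks from first dose. This follows the two time origins in SAP 3.1.1 and 3.1.2 and costs a sentence or two.
3. Reconcile the Week 12 visit window with Table 3 in one of two ways. Either start the visit window at Protocol Day 63 (SAP Day 64), which takes 7 days of flexibility from sites, or move the Table 3 boundary so that Week 6 ends on SAP Day 56 and Week 12 begins on SAP Day 57. The second needs no Protocol change and still contains every on-time Week 6 visit (SAP Days 40 to 46).

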9.2.1.2 Key Secondary Efficacy Analysis

The key secondary endpoint is the time to resolution of bladder pain as measured by age-appropriate COAs. Resolution of pain is defined as participants achieving a score on the relevant COA that does not exceed "mild pain" (defined in Section 7) without use of prescription pain medications or supportive bladder care.

If the result of the analyses of the primary efficacy endpoint (ie, time to resolution of macroscopic hematuria) is statistically significant based on both the BK ITT and overall ITT Populations, a formal hypothesis test will be conducted sequentially of the time to resolution of bladder pain based on the BK ITT Population in the same manner as described for the primary efficacy analysis of the primary efficacy endpoint, except that a 0.025 significance level will be used. Additional analyses of the time to resolution of bladder pain will also be performed based on the BK mITT and BK PP Populations as sensitivity analyses.

If this result of the analysis of time to resolution of bladder pain based on the BK ITT Population is statistically significant, a formal hypothesis test of this endpoint will then be conducted based on the overall ITT Population using a 0.025 significance level. A sensitivity analysis will be conducted based on the mITT Population.

